# Clinical Study Protocol

## Johnson & Johnson Vision Care, Inc.

### 14.2. Sample Size Justification

This study was designed and powered to test for superiority of the Test lens after 1-week of optimized lens wear with respect to the following: binocular HLHC visual performance at distance, intermediate and near, subjective Vision scores for both the hyperopic and myopic groups grade 3 or higher slit lamp findings and unacceptable lens fitting. Additionally, this study was also powered to test for superiority with respect to CLUE Comfort and Handling and Lens Fit success.

The sample size for co-primary efficacy endpoints was estimated to achieve a minimum statistical power of 99% for visual performance and CLUE Vision using a 2-sided type I error rate of 1%. Co-primary safety endpoints (slit lamp findings and unacceptable lens fitting) were estimated to achieve a minimum statistical power of 90% with 95% central posterior credible interval. The sample size for secondary endpoints (with the exception of lens fit success) were estimated to achieve a minimum statistical power of 80% using a two-sided type I error rate of 1% each. a minimum statistical power of 80% for lens fit success with the 99% central posterior credible interval.

With respect to safety endpoints, historical data from 7 studies were utilized, however, for primary efficacy and secondary endpoints historical data from only two studies were utilized in the sample size calculation since there were the only studies that have completed after design-lock (Phase2b). A summary of historical studies utilized in the sample size calculation are summarized in Table 6 below. For the sample size estimate for this study, only data from period 1 was utilized. Table 7 below summaries the historical data by endpoint.

Table 6: Historical Studies Utilized for Sample Size Calculations

Study Number	Design	Population	Number Enrolled	Number in Safety Population	Number in PP population	Endpoints utilized for sample size
[REDACTED]	2x2	Myopes	34	33	30	Primary Safety
	2x2	Hyperopes	48	44	41	Primary Safety
	2x3	Hyperopes	81	78	67	Primary Safety
	2x3	Myopes	71	68	60	Primary Safety
	2x3	Hyperopes	78	75	64	Primary Safety, Efficacy, Secondary
[REDACTED]	2x3	Myopes	81	78	66	Primary Safety, Efficacy, Secondary
[REDACTED]	2 Phase 3x3	Hyperopes	40	37	34	Primary Safety

PP: Per-Protocol

# Clinical Study Protocol

## Johnson & Johnson Vision Care, Inc.

Table 7: Historical Data by Endpoint

Endpoint Type	Endpoint	Data Type	Value
*Primary Efficacy	VP - Distance	Mean (SD)	-0.109 (0.0848)
	VP - Intermediate		-0.024 (0.1129)
	VP - Near		0.085 (0.1264)
	CLUE Vision (Hyperopes)		57.1 (17.27)
	CLUE Vision (Myopes)		60.6 (16.84)
**Primary Safety	Grade 3 + SLF (Adverse Event)	Rate	0.24% (1 eye)
	Unacceptable Lens Fitting		0% (0 eye)
*Secondary	CLUE Vision Hyperopes	Mean (SD)	57.1 (17.27)
	CLUE Vision Myopes		60.9 (16.65)
	CLUE Comfort (Hyperopes + Myopes)		72.3 (17.43)
	CLUE Handling (Hyperopes + Myopes)		71.7 (17.09)
	Lens Fit Success	Rate	100%

VP: Visual Performance, SD=Standard Deviation

\*Summaries for primary efficacy and secondary endpoints were provided for the per-protocol population at the 1-week follow-up evaluation for period 1 only.

\*\* Summaries for the primary safety endpoints were provided for the safety population; all available data was included

### Primary Safety Endpoint Sample Size Calculations:

#### Grade 3 or Higher Slit Lamp Findings (SLF) and Unacceptable Lens Fitting

Sample size estimates for SLFs grade 3 or higher and unacceptable lens fitting were calculated using the same technique and assumptions. Since both safety endpoints are testing against a 5% threshold and have an event rate less than 0.5% both endpoints require the same sample to achieve the same pre-specified confidence level of 95%. Furthermore, it should be noted that why both endpoints are collected on all subjects they are clinically independent.

For Grade 3 or Higher SLF was converted to a binary response as  $Y = 1$  if a subject eye has a clinically significant SLF and  $Y = 0$  otherwise for analysis purpose (Unacceptable lens fitting is derived as a binary response as  $Y=1$  is a subject had an unacceptable lens fit and 0 otherwise). From the historical data there was no/extremely low rate ( $< 1\%$ ) for clinically significant SLFs (Grade 3 or higher) or unacceptable lens fitting for the study lens. Assuming a correlation of 0.70 between left and right eyes within the same subject, a total of 2000 replicating trials were simulated with a reference rate of 2% (worse-case scenario). Given the rare event binary outcome of slit lamp findings, (or unacceptable lens fit) each replicated sample was analyzed using a Bayesian beta-binomial model with correlated binary data (Diniza et al; 2010). For each simulated trial, the upper bound of the 95% central posterior credible interval constructed for the percentage of Grade 3 or higher SLFs for the Test lens was compared to a margin of 5%. With the proposed sample size, there was at least 90% of the estimated 95% credible intervals with the upper bound being below 5%.

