#### Lens Fit Success

Lens fit success was converted to a binary response as  $Y = 1$  if lens optimization was achieved in 4 lenses or less and  $Y = 0$  otherwise for analysis purposes. From the historical data there was 100% rate for lens fit success there for a worst-case scenario of 98% was used as the reference rate. Assuming a correlation of 0.70 between left and right eyes within the same subject, a total of 2000 replicating trials were simulated. Given the rare event binary outcome,  $Y=0$  each replicated sample was analyzed using a Bayesian beta-binomial model with correlated binary data (Diniza et al; 2010). For each simulated trial, the lower bound of the 99% central posterior credible interval constructed for the percentage successful lens fit for the Test lens was compared to a margin of 90%. With the proposed sample size, there was at least 80% of the estimated 99% credible intervals with the lower bound being above 90%.

Table 8 displays the sample size estimates and associated power by endpoints. As indicated below, co-primary safety endpoints were powered ~92% individually yielding a combined power of ~84%. With respect to co-primary efficacy each hypothesis was powered to ~99% power provided a combine power of ~95%. Therefore, the overall combined study power for co-primary safety and co-primary efficacy hypotheses is ~79% and is considered reasonable to support any conclusions from these analyses. Furthermore, secondary endpoints were powered to achieve at least 80% statistical power. This was considered to have a minimal impact on overall study power because of the multibranch gate keeping approach being implemented.

Table 8: Sample Size Estimates by Endpoint

Endpoint Type	Endpoint	Test Type	Sample Size	Power (%)
Primary Efficacy	VP - Distance	Superiority (0.00)	17	99.4
	VP - Intermediate	Superiority (0.17)	11	99.3
	VP - Near	Superiority (0.17)	48	99.0
	CLUE Vision-Hyperopes	Superiority (36)	14	99.4
	CLUE Vision Myopes	Superiority (41)	18	99.0

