# Clinical Study Protocol

## Johnson & Johnson Vision Care, Inc.

Endpoint Type	Endpoint	Test Type	Sample Size	Power (%)
Primary Safety	Grade 3 + SLF	Statistically less than (5%)	100	92.6
	Unacceptable Lens fitting	Statistically less than (5%)	100	92.6
Secondary	CLUE Vision-Hyperopes	Superiority (41)	16	82.4
	CLUE Vision Myopes	Superiority (46)	15	82.3
	CLUE Comfort (Hyperopes + Myopes)	Superiority (52)	11	83.8
	CLUE Handling (Hyperopes + Myopes)	Superiority (53)	17	83.7
	Lens Fit Success	Superiority (90%)	92	82.1

Based on the table above a total of at least 100 subjects a required to complete the study. To account for screen failures and subject dropout Up to 120 subjects (72 myopes and 48 hyperopes) will be enrolled to ensure at least 100 (60 myopes and 40 hyperopes) complete the study.

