### 14.3. Analysis Populations

#### **Safety Population:**

All subjects who were administered any test article excluding subjects who drop out prior to administering any test article. At least one observation should be recorded.

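### At the 2% worst-case rate the protocol says it simulated, each co-primary safety test has about 55% power with 100 subjects, not 92.6%, so the combined figures of about 84% and 79% are also wrong

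*Combined protocol and SAP*

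**What the plan says.** Section 14.2 of the protocol says that the co-primary safety endpoints (Grade 3 or higher slit lamp findings, and unacceptable lens fit) "were estimated to achieve a minimum statistical power of 90% with 95% central posterior credible interval". The simulation is described in the same section under the safety endpoint heading. With a between-eye correlation of 0.70, "a total of 2000 replicating trials were simulated with a reference rate of 2% (worse-case scenario"). Each simulated trial was analysed with the correlated beta-binomial model and passed if the upper limit of the 95% central credible interval was under the 5% margin. The reported result is: "With the proposed sample size, there was at least 90% of the estimated 95% credible intervals with the upper bound being below 5" per cent.

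Table 8 gives 92.6% power with 100 subjects for each safety endpoint. The text before the table carries this forward: "co-primary safety endpoints were powered ~92% individually yielding a combined power of ~84" per cent, and then "the overall combined study power for co-primary safety and co-primary efficacy hypotheses is ~79" per cent. After the table comes the sample size: "Based on the table above a total of at least 100 subjects a required to complete the study".

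Section 14.5 uses the same model and decision rule for the analysis and gives the priors. The analysis set is the safety population of section 14.3: "All subjects who were administered any test article excluding subjects who drop out prior to administering any test article".

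**The concern.** A true rate of 2% is not far below a 5% margin when only 100 subjects, with strongly correlated eyes, contribute. On average 4 of 200 eyes would be affected, mostly as bilateral pairs, and a 95% upper limit around that count is already close to 5%. Power above 90% looked implausible.

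The safety rows are the largest in Table 8, so they set the 100 completers. Under sections 2.3 and 14.4 both safety tests must pass before any efficacy or secondary hypothesis is tested. A reader is told that this first step holds with at least 90% power per test even in the worst case, and the overall power that the protocol calls reasonable is built on that statement.

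**Working it through.** **Inputs.** Rate p = 0.02 per eye, correlation ρ = 0.70, N = 100, and pass if the 97.5th posterior percentile of p is below 0.05 (section 14.2). The likelihood is the section 14.5 mixture. The priors are also from section 14.5: N(0, 1000) on the logit intercept and beta(0.5, 0.5) on ρ. The lens coefficient is dropped because a single arm cannot identify it. Section 14.2 does not state the simulation's priors, so using those of section 14.5 is an assumption.

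**The protocol's combined figures.** These follow roughly from their parts: 0.92² = 0.846 and 0.84 × 0.95 = 0.798. The error is therefore in the 92.6%, not in the multiplication.

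**Probabilities per subject.**
- Both eyes: p² + ρp(1−p) = 0.0004 + 0.70 × 0.0196 = 0.01412
- One eye: 2(1−ρ)p(1−p) = 2 × 0.30 × 0.0196 = 0.01176

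**A bound that hardly depends on the priors.** With 100 subjects, the probability of three or more bilateral cases is 16.8%. Three bilateral cases and nothing else give an upper limit of 6.7% under the section 14.5 model. Even treating them as 6 of 200 independent eyes, Beta(6, 194), the limit is 5.8%. All these outcomes fail, so power cannot exceed 100 − 16.8 = 83.2%.

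**Exact power.** For every pair (subjects with one eye affected, subjects with both affected), the posterior was computed on a grid, and each passing outcome was weighted by its multinomial probability. The outcomes that pass at N = 100 are:

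| One eye, both eyes | Probability |
|---|---|
| 0, 0 | 0.0727 |
| 1, 0 | 0.0877 |
| 2, 0 | 0.0524 |
| 3, 0 | 0.0207 |
| 4, 0 | 0.0061 |
| 0, 1 | 0.1053 |
| 1, 1 | 0.1259 |
| 2, 1 | 0.0745 |
| **Sum** | **0.545** |

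A 2000-trial Monte Carlo run of the same model gave 55.1%. Two outcomes lie almost on the line: (2, 1) passes with an upper limit of about 4.95%, and (0, 2), probability 0.0756, fails with about 5.07%. Switching one or the other gives 47.1% or 62.1%.

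**Other readings at 2%.**

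| Reading | N = 100 | N = 120 |
|---|---|---|
| As stated | 54.5% | 63.2% |
| One-sided 95% bound | 62–65% | 74.7% |
| True correlation 0 | 62.9% | 65.1% |
| One-sided bound and correlation 0 | 78–79% | 79% |
| Beta(0.5, 0.5) prior on p | 46.5% | 50.4% |
| Uniform prior on p | 33.9% | 36.1% |
| 80% interval instead of 95% | 83.7% | 83.3% |

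The most favourable variant tried drops the correlated model altogether: 240 independent eyes, a near-improper prior and a one-sided 95% bound. It gives 88.9%.

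**Power by true rate, section 14.5 model, ρ = 0.70.**

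| Rate per eye | N = 100 | N = 120 |
|---|---|---|
| 0.24% | 98.7% | 99.9% |
| 0.5% | 95.1% | 98.8% |
| 1% | 83.6% | 92.0% |
| 1.5% | 69.2% | 79.2% |
| 2% | 54.5% | 63.2% |

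The stated 92.6% is reached at about 0.63% (N = 100) or 0.97% (N = 120).

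**Combined, as independent tests.** At N = 100, 0.545² = 0.297 (0.471² = 0.22 to 0.621² = 0.39). At N = 120, 0.632² = 0.40. Each efficacy test exceeds 99.99% at the planned 100/60/40 completers, so overall power at 2% is essentially the same product.

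**Side note on the efficacy rows.** Table 7 inputs, Table 8 sample sizes and a two-sided 1% t-test give 98.4% (distance), 98.3% (intermediate), 97.2% (near), 91.8% (CLUE hyperopes) and 96.9% (CLUE myopes). Their product is 83.6%, not about 95%. This has little consequence at the planned completers.

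**The case against.** The strongest objection is about weight. Power does not enter the test: pass or fail depends on the observed data against 5%. The protocol itself expects far less than 2%: "Since both safety endpoints are testing against a 5% threshold and have an event rate less than 0.5" per cent. The historical slit lamp rate may be lower still. The safety populations in Table 6 sum to 33 + 44 + 78 + 68 + 75 + 78 + 37 = 413 subjects, and 1/413 = 0.24%, so Table 7 appears to divide one eye by subjects. Per eye that is about 0.12%, where power at N = 100 is 99.7%. This stands, and it means the trial is not shown to be underpowered at the rates it expects. It does not make the 2% statement true.

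Second, the safety population should exceed 100. Table 6 shows 413 of 433 enrolled subjects in the safety populations (95%), which for 120 enrolled is about 114. Power at 2% is then likely to lie between 55% and 63%. This also stands, but Table 8 labels the row 100, and neither figure is near 90%.

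Third, the sponsor's simulation may have used settings not shown. The same calculation on the lens-fit row gives 88.7% against a stated 82.1%, a miss in the other direction, and the zero-event model is deferred to the stand-alone SAP. Zero events has probability 7.3% and is counted here as a pass, so a different model for that case could not raise the result. Undisclosed settings are a reason to ask for a rerun with disclosure rather than to insist on exactly 54.5%. They do not rescue 90% at N = 100, given the 83.2% ceiling.

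**Conclusion.** The concern holds. With the inputs in section 14.2 and the model in section 14.5, power per safety test at 2% is about 55% (47% to 62%) with 100 subjects and about 63% with 120, against the stated 92.6%. Power for both tests, and overall, is about 30% (N = 100) or 40% (N = 120), against about 84% and 79%. These figures assume the section 14.5 priors, no lens term and independent endpoints as in the protocol. That power falls short of 90% with 100 subjects does not depend on the choice among the priors examined. At true rates up to 0.5% per eye, power is 95% or more. What fails is the claim that the design keeps at least 90% power at the worst-case rate.

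**What to change.** Rerun the safety simulation and state its priors and its handling of zero events. In section 14.2 and Table 8, either report the power that the rerun gives at 2% (about 55% per endpoint at N = 100 on the section 14.5 priors), or state the rate at which about 93% holds (about 0.6% at N = 100, about 1% at N = 120). In either case show power over 0.24% to 2% for 100 and 120 subjects, and say whether the historical 0.24% is per eye or per subject. Replace the 84% and 79% with products of the corrected values. As a tidy-up, restate the efficacy rows at 100/60/40 completers and two-sided 1%.

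The cost is a short rerun and changed wording. The stated worst-case power becomes less favourable. No change is needed to sample size, endpoints, decision rule or analysis. For scale only, 90% power at 2% would need about 300 subjects (88.6% at 280, 91.1% at 300).

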### Primary Efficacy Endpoint Sample Size Calculations:

# Clinical Study Protocol

## Johnson & Johnson Vision Care, Inc.

### Binocular HLHC Visual Performance and CLUE Vision Scores

Sample size calculations for each co-primary efficacy endpoint were carried separately out using a 2-sided one sample mean t-test, with a two-sided type I rate of 1%. The calculation was performed using the POWER procedure in SAS Version 9.4.

### **Secondary Endpoint Sample Size Calculations:**

#### CLUE Vision, Comfort and Handling

Sample size calculations for each secondary endpoint (with the exception of lens fit Success) were carried separately out using a 2-sided one sample mean t-test, with a two-sided type I rate of 1%. The calculation was performed using the POWER procedure in SAS Version 9.4.

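### Table 8's t-test powers do not follow from Table 7 at the declared two-sided 1%: eight of nine rows miss their stated minimum, though enrolment is unaffected

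*Combined protocol and SAP*

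**What the plan says.** Section 14.2 describes the method for both tiers of continuous endpoints. For the secondary CLUE endpoints it says the calculations were "carried separately out using a 2-sided one sample mean t-test, with a two-sided type I rate of 1"%. Co-primary efficacy is described in the same terms, and for both tiers the software is SAS: "The calculation was performed using the POWER procedure in SAS Version 9.4".

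The power targets are a "minimum statistical power of 99% for visual performance and CLUE Vision using a 2-sided type I error rate of 1"% for the co-primary efficacy endpoints. The secondary endpoints other than lens fit success "were estimated to achieve a minimum statistical power of 80% using a two-sided type I error rate of 1% each".

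Table 7 gives the historical means and SDs. Table 8 gives the threshold, sample size and power for each endpoint. The text before Table 8 multiplies the rows into a combined efficacy power of ~95% and an overall power of ~79%, and adds: "Furthermore, secondary endpoints were powered to achieve at least 80% statistical power".

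Table 7 lists myope CLUE Vision twice, as 60.6 (16.84) under primary efficacy and as 60.9 (16.65) under secondary. Its footnote gives one population and visit for both: per-protocol, 1-week, period 1.

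**The concern.** All the inputs to these nine rows are printed, so the powers should be reproducible to within rounding. They are not. If the listed sample sizes do not deliver the claimed minimums at the declared alpha, three statements in section 14.2 are wrong as written: the 99% minimum, the 80% minimum, and the combined ~95% and ~79%. The last pair matters most, because the protocol uses it to call the study's power reasonable. The two myope entries in Table 7 add an ambiguity, since the same quantity feeds the primary and secondary rows with different values.

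**Working it through.** **Inputs.** Means and SDs come from Table 7. Thresholds, n and stated power come from Table 8. The test and alpha come from the primary efficacy and secondary subsections of 14.2.

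**Formula.** Effect size d = |mean − threshold| / SD. Noncentrality = d√n, with n − 1 degrees of freedom. Power is the probability that a noncentral t variable exceeds the two-sided critical value t(1 − α/2, n − 1) in absolute value.

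**Worked row: CLUE Vision, hyperopes against 36.** d = (57.1 − 36)/17.27 = 1.222. With n = 14 the noncentrality is 1.222 × √14 = 4.57. The critical value at two-sided 1% on 13 df is 3.012. Power is 91.8%, against a stated 99.4%. To reach 99.4% at n = 14, d would have to be 1.575, which corresponds to a threshold near 29.9 rather than 36. Rounding in Table 7 cannot account for that.

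**All nine rows** (power in %). The 1% column was confirmed with 200,000 simulated trials per endpoint.

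| Endpoint (threshold) | d | Listed n | Stated | 1% | 2% | 5% | n needed at 1% |
|---|---|---|---|---|---|---|---|
| Distance VA (0.00) | 1.285 | 17 | 99.4 | 98.4 | 99.4 | 99.9 | 19 |
| Intermediate VA (0.17) | 1.718 | 11 | 99.3 | 98.3 | 99.4 | 99.9 | 12 |
| Near VA (0.17) | 0.672 | 48 | 99.0 | 97.2 | 98.6 | 99.5 | 57 |
| CLUE Vision hyperopes (36) | 1.222 | 14 | 99.4 | 91.8 | 96.0 | 98.8 | 20 |
| CLUE Vision myopes (41) | 1.164 | 18 | 99.0 | 96.9 | 98.6 | 99.6 | 22 |
| CLUE Vision hyperopes (41) | 0.932 | 16 | 82.4 | 76.9 | 85.5 | 93.6 | 17 |
| CLUE Vision myopes (46) | 0.895 | 15 | 82.3 | 68.3 | 78.7 | 89.6 | 18 |
| CLUE Comfort (52) | 1.165 | 11 | 83.8 | 73.8 | 84.1 | 93.5 | 13 |
| CLUE Handling (53) | 1.094 | 17 | 83.7 | 92.7 | 96.3 | 98.8 | 14 |

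The myope rows use the Table 7 entry for their own tier. Exchanging the pairs changes the n needed from 22 to 21 (primary, 60.9/16.65) and from 18 to 19 (secondary, 60.6/16.84).

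At the declared 1%, all five co-primary rows are below 99% and three of the four secondary rows are below 80%.

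**Combined power.** The protocol's own figures first: five rows at 99% give 0.99⁵ = 95.1%, its ~95%, and its ~84% for safety times 95% gives 79.8%, its ~79%. With the recomputed rows, 0.984 × 0.983 × 0.972 × 0.918 × 0.969 = 0.836, about 84%. Multiplying by 0.926 × 0.926 = 0.857 for the two safety rows of Table 8 gives 0.717, about 72%. With the protocol's rounded 84% for safety it is 0.836 × 0.84 = 0.702, about 70%.

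**Power at the planned completers, two-sided 1%.** Hyperopes against 41 at N = 40: 99.89%. Near VA at N = 100: 99.997%. Myopes against 46 at N = 60: 99.998%. Every other row is above 99.999%.

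**The case against.** The strongest reply is that nothing in the trial turns on these rows. The 100 completers come from the two safety endpoints, and lens fit success needs 92. No t-test row needs more than 57 subjects even after correction. At 40 hyperopes, 60 myopes and 100 pooled, all nine rows are powered far beyond their targets, so on the efficacy side the ~95% understates the trial as planned. This stands, and it limits the point to a correction of the sample size justification.

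A second reply is that the decision rules in sections 14.5 and 14.6 use 95% intervals for these endpoints, not 99%. At two-sided 5% the listed n meet every minimum except hyperopes against 36 (98.8% against 99%). That is correct, but section 14.2 declares 1% and section 14.4 assigns 1% per test. Nor does 5% reproduce the printed powers: comfort would be 93.5%, not 83.8%.

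The rows are also of unequal weight. The visual performance rows miss by 1.0, 1.0 and 1.8 points, primary myopes by 2.1, and handling is better than stated.

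A reader might infer that the table was simply run at two-sided 2% (one-sided 1%). That matches distance and comes close for intermediate and comfort. It leaves near at 98.6% (stated 99.0%) and hyperopes against 36 at 96.0% (stated 99.4%). It fits other rows only if the two secondary CLUE Vision sample sizes are exchanged, the secondary myope mean is used in the primary row, or handling is taken at n = 12. The handling clue is not unique either: 83.7% also arises at n = 14 with two-sided 1%. The documents do not support any one explanation.

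**Conclusion.** The point holds as a reproducibility failure in Table 8. At the declared two-sided 1%, eight of nine t-test rows miss their claimed minimum. The shortfall against the stated power runs from 1 point (distance and intermediate acuity) to 14 points (myopes against 46). The material misses are four CLUE rows: hyperopes against 36, both secondary vision rows, and comfort. Combined power at the listed n is about 84% for efficacy and 72% overall on the protocol's own multiplication.

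No single alpha among 1%, 2% and 5% reproduces the table, so the cause cannot be settled from the documents. A reader might also infer that the trial is underpowered for efficacy. It is not: power at the planned numbers is at least 99.89% for every row.

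The figures assume the Table 7 means and SDs as printed and normally distributed scores. The combined figures also assume independence between endpoints, as the protocol's multiplication does, and take the 92.6% safety powers from Table 8 without rechecking them.

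**What to change.** 1. Choose one myope CLUE Vision mean and SD for Table 7, 60.6 (16.84) or 60.9 (16.65), and use it in both tiers.
2. Reconcile the 1% per test in section 14.4 with the 95% intervals in sections 14.5 and 14.6, then rerun the nine t-test rows at the alpha that will be used.
3. If that alpha is two-sided 1%, the required n are 19, 12, 57 and 20 for distance, intermediate, near and primary hyperopes, and 22 for primary myopes (21 with 60.9/16.65). For the secondary endpoints they are 17 for hyperopes, 18 for myopes (19 with 60.6/16.84), 13 for comfort and 14 for handling. If different inputs were in fact used, state them.
4. Restate the combined power in the text before Table 8, preferably from power at the planned 40, 60 and 100, and add that as a column.

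The cost is a correction to two tables and one paragraph. No additional subjects are needed.
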